Progression-Free Survival (PFS) is defined as the time from randomization to first documentation of objective tumor progression (progressive disease [PD], radiological) according to RECIST (Version 1.1) or death due to any reasons whichever comes first. PFS data will be censored on the day following the date of last tumor assessment documenting absence of PD for subjects who do not have objective tumor progression and are still on study at the time of the analysis, are given anti-tumor treatment other than the study treatment, or are moved from treatment follow-up prior to documentation of objective tumor progression. Subjects having no tumor assessments after randomization who are not known to have died will have PFS censored on the date of randomization.

Overall survival (OS) is defined as the time from the date of randomization to date of death due to any cause. In the absence of confirmation of death, survival time will be censored at the last date the subject is known to be alive. Subjects lacking data beyond randomization will have their survival times censored on the date of randomization.

Overall response rate (ORR) is defined as the proportion of subjects with confirmed CR or confirmed PR according to RECIST (Version 1.1), relative to the total population of randomized subjects. Confirmed responses are those that persist on repeat imaging study at least 4 weeks after the initial documentation of response.

Duration of response (DoR) is defined as the time from the first documentation of objective tumor response to the first documentation of objective tumor progression or to death due to any cause. DoR data will be censored on the day following the date of the last tumor assessment documenting absence of PD for subjects who do not have tumor progression and are still on the study at the time of an analysis, are given antitumor treatment other than the study treatment, are removed from the study follow-up prior to documentation of objective tumor progression, died of non-cancer related cause, including death due to unknown cause in the absence of documented disease progression. **DoR will only be calculated for the subgroup of subjects with an objective tumor response (PR or CR).**

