4.7.1.3 Handling of Dropouts or Missing Data

In general, imputed partial dates will not be used to derive study day, duration (e.g., duration of adverse events), or elapsed time variables. In addition, imputed dates are not used for deriving the last contact date in the overall survival analysis dataset.

Imputed dates will not be displayed in listings unless otherwise stated.

The partial date imputation will follow ADaM conventions. The ADaM approach is to populate the numeric date variables with the imputed date and add a flag variable to the dataset that indicates the level of imputation.

The flag variable can contain the values: blank, 'D', 'M', 'Y'.

blank: indicates that no imputation was done

- D='Day': indicates that the day portion of the date is imputed
- M='Month': indicates that the month and day portions of the date are imputed
- Y='Year': indicates that the entire date (year, month, and day) is imputed

Imputing partial AE and prior/concomitant medication start dates:

- a) If the year is unknown, the date will not be imputed and will be assigned a missing value.
- b) If the month is unknown, then:
 - 1. If the year matches the first dose date, then impute to the month and day of the first dose date.
 - 2. Otherwise, assign 'January'.
- c) If the day is unknown, then:
 - 1. If the month and year match the first dose date, then impute to the day of the first dose date.
 - 2. Otherwise, assign '01'.

Imputing partial AE and prior/concomitant medication stop dates:

- a) If the year is unknown, the date will not be imputed and will be assigned a missing value.
- b) If the month is unknown, then assign 'December'.
- c) If the day is unknown, then impute to the last day of the month.

Imputing partial death dates:

- a) If the month and/or year are unknown, the death date will not be imputed and the subject will be censored for overall survival at the last known date alive.
- b) If the day is missing, then assign '01'.
- c) If imputing the first day of the month results in a negative overall survival time, the subject will be censored for overall survival at the randomization date.

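### The rules for death dates with a missing day can turn a recorded early death into censoring at randomization, and can date a death before the subject was last known alive

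*SAP*

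**What the plan says.** SAP 4.7.1.3 gives three rules for partial death dates.

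- **Rule (a), month or year unknown:** "the death date will not be imputed and the subject will be censored for overall survival at the last known date alive".
- **Rule (b), only the day missing:** the day is set to 01. No other condition is attached.
- **Rule (c):** "If imputing the first day of the month results in a negative overall survival time, the subject will be censored for overall survival". The censoring date is the day of randomization.

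The section also says that "imputed dates are not used for deriving the last contact date in the overall survival analysis dataset". This keeps imputed dates out of the last contact date. It does not stop an imputed death date from falling before that contact.

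The endpoint definitions start from a different principle. Protocol 14.3.4 defines OS as time from randomization to death from any cause and adds: "In the absence of confirmation of death, survival time will be censored at the last date the subject is known to be alive". SAP 3.2.1 likewise ties last-known-alive censoring to the lack of a confirmed death. It computes OS as death date minus randomization date plus one day, converted to months.

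**The concern.** A randomized subject cannot have died before randomization. If month and year of death are known and rule (b) gives a negative time, the error lies in the assumed day. Rule (c) does not correct the day. It drops the death and leaves the subject with no follow-up. Whether a subject is censored then depends on the event itself having happened early, which is not a sound ground for censoring.

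Rule (b) has a related flaw: it can contradict a documented contact later in the same month. The same SAP section already avoids this problem for adverse event and medication start dates. Those go to the first-dose day when month and year match it, and to the 1st only otherwise. Death dates have no equivalent bound.

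OS is the first secondary endpoint. The earlier tivozanib versus sorafenib trial described in Protocol 3.6.2 had an OS hazard ratio of 1.245 in favor of sorafenib. OS will be read closely here, and a rule that removes recorded deaths is hard to defend.

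**Working it through.** **Planning figure.** SAP 4.9 gives 245 deaths at the final OS analysis, medians of 12 and 16 months (hazard ratio 12/16 = 0.75), one-sided 2.5%, and about 61% power. By Schoenfeld's formula, z = sqrt(245/4) x |ln 0.75| - 1.96 = 7.826 x 0.2877 - 1.96 = 0.29, so power is 61.5%. The plan's figure is reproduced.

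**When rule (c) applies.** For a death in the randomization month, set to the 1st, with randomization on day d:

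OS days = 1 - d + 1 = 2 - d

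| Randomized on day | OS days | Result |
|---|---|---|
| 1 | 1 | event |
| 2 | 0 | event at time zero |
| 3 | -1 | censored at randomization |
| 15 | -13 | censored at randomization |
| 31 | -29 | censored at randomization |

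**How many subjects die in that window.** Exponential survival with the planned medians and uniform accrual from June 2016 to August 2017 was simulated. The probability is 2.6% on sorafenib and 1.9% on tivozanib, or 161 x 0.0263 + 161 x 0.0191 = 4.2 + 3.1 = 7.3 of 322.

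A first-order hand check with a 30-day month agrees:
- Average exposed days over all randomization days, counting only days 3 to 30: (28 + 27 + ... + 1)/30 = 406/30 = 13.5.
- Daily hazards: ln 2/365.25 = 0.00190 (12 months) and ln 2/487 = 0.00142 (16 months).
- Probabilities: 2.6% and 1.9%, giving 4.1 + 3.1 = 7.2 subjects.

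**How many are affected.** Only deaths with a missing day count, and the documents give no such share. The shares below are assumptions.

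| Assumed share of deaths with day missing | Censored at randomization (share x 7.3) | Set to the 1st (share x 245) |
|---|---|---|
| 2% | 0.15 | 5 |
| 5% | 0.4 | 12 |
| 10% | 0.7 | 25 |
| 20% | 1.5 | 49 |

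**Early dating under rule (b).** For a death in a later month than randomization, the 1st is on average 14.6 days too early. A subject last seen on the 20th who died later that month is dated dead 19 days before that contact. Under rule (b), the share of imputed dates that fall before last known alive depends on the timing of the last contact. It is about 16%, 47% or 85% if that contact was uniformly within 91, 30 or 7 days of death (assumed).

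**Effect on power.** The same formula gives 61.3% with one death lost, 61.1% with two and 60.6% with five. In the extreme case of eight lost, which is more than the 7.3 expected in the window, it gives 60.0%.

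**The case against.** The best counter-argument is about size, and much of it stands.

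- **Early deaths are the ones most likely to be fully dated.** Protocol 12.6.2 requires any death within 30 days of last dose to be reported within 24 hours of awareness, and 12.6.5 lists the date of death in the notification. The three-monthly survival contact starts only after the 30-Day Follow-up Visit, so it is no reason to expect many missing days in the randomization month. The upper rows of the table are therefore unlikely for rule (c), and a count near zero is plausible.
- **Entry criteria reduce very early deaths.** Life expectancy of at least 3 months and ECOG 0 or 1 make a constant hazard pessimistic.
- **The rules are the same in both arms**, and SAP 4.7.1.4 calls the secondary analyses supportive.
- **First-of-month is a convention.** It contradicts recorded data only when a contact falls later in that month, so it would be wrong to infer that every death dated this way is in error.
- **The protocol contains no explicit ban.** It does not say that censoring is allowed only without confirmation of death, and it also censors at randomization subjects with no data beyond that date. A recorded death is such data, however, so that sentence does not cover rule (c).

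One could add that rule (c) changes little, because the first OS bullet in SAP 3.2.1 censors at randomization anyone without a later tumor assessment, and the first scan is due at 8 weeks. Read literally, that bullet would reach many of the same subjects. It does not justify rule (c), but it must be aligned if these deaths are to be kept.

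None of this defends the derivation itself. Nothing in either document restores the lost death or bounds the imputed date.

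**Conclusion.** The point holds as a defect in a stated derivation. Rule (c) converts a recorded death into a non-event at time zero for a day-missing death in the randomization month when randomization was on day 3 or later. Rule (b) allows a death date earlier than documented survival. The first result conflicts with the OS definition in both documents, and the second can conflict with the subject's own data.

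The size is probably small. About 7 of 322 subjects fall in the rule (c) window under the planned medians and exponential survival, and only those with a missing day are affected. Losing up to five deaths costs less than one point of OS power.

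Two stronger readings are tempting and not supported:

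- **That the rules bias the OS comparison or weaken it materially.** No direction of bias between arms can be shown from the documents, and the power loss is negligible.
- **That they produce impossible PFS times.** Death is a PFS event, but the SAP does not say that these rules apply to PFS. Rules (a) and (c) name only OS. The section also says that imputed dates are in general not used for elapsed-time variables, while its closing text mentions imputed dates in the primary analysis without saying which. PFS handling is unspecified, and no more than that can be said.

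Rule (a) also censors known deaths, but with the month unknown neither choice is clearly better. Censoring discards an event, and imputing just after last contact may date it months too early.

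**What to change.** In SAP 4.7.1.3:

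1. When month and year of death are known, keep the death as an OS event. Set the date to the latest of the conventional day (the 1st may stay), the randomization date and the day after last known alive, but no later than the last day of the reported month.
2. Delete the censoring in rule (c), which is then never needed.
3. State that the same bounded date is used when death is the PFS event.
4. For confirmed deaths with unknown month, rule (a) may stay as the main rule. Add a sensitivity analysis that counts them as events.
5. Align the first OS bullet in SAP 3.2.1, so that a recorded death is not censored merely because no scan followed randomization.

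The cost is a few lines of SAP text and programming. No new data are needed, because the randomization and last-contact dates are already collected. With every such death kept, OS power stays at 61.5% for 245 deaths.

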4.7.1.4 Multiple Comparisons/Multiplicity

There will be no adjustment for multiplicity. PFS with one treatment contrast (tivozanib vs. sorafenib) is the only primary analysis defined for this study. The secondary analyses are simply intended to provide supportive evidence relating to the primary analysis, therefore, all efficacy endpoints will be assessed without adjustment for multiple comparisons.

4.7.1.5 Interim Analyses

An interim analysis will be performed after 128 PFS events have been observed. The interim analysis will look into the study's futility with PFS as the efficacy evaluation endpoint. This utilizes a Lan-DeMets spending-type function with an O'Brian-Fleming stopping boundary and estimated two-sided beta (Type II error) of 1.2% spent during this interim look. A planned futility analysis will also be performed.

This interim and futility analyses will be performed by an independent statistician. The independent statistician will evaluate and interpret the results of the interim and futility analyses and will provide corresponding recommendation. The recommended outputs for this reporting effort will be listed in a separate document.

4.7.1.6 Examination of Subgroups

The uniformity of the treatment effect for the primary efficacy variable will be examined for the following subgroups:

- 1. Age categorization (<65 years, >=65 years)
- 2. Gender (Male, Female)
- 3. Race (White, Non-White)
- 4. Baseline Eastern Cooperative Oncology Group (ECOG) performance status (0, 1)
- 5. Time from initial diagnosis to randomization (< 1 year, >=1 year)
- 6. Geographic region [North America (NA), European Union (EU), Rest of World]
- 7. IMDC risk category (Favorable, Intermediate, Poor)
- 8. Prior therapy (Two Prior VEGFR TKIs, Prior Checkpoint Inhibitor Plus VEGFR TKI, Prior VEGFR TKI Plus Other Systemic Agent)
- 9. Number of metastatic sites involved $(1, \ge 2)$
- 10. Baseline systolic blood pressure (<=140 mmHg, >140 mmHg)
- 11. Baseline diastolic blood pressure (<=90 mmHg, >90 mmHg)

The homogeneity of the treatment effect across subgroups will be investigated using graphical method showing the median treatment effect and 95% confidence interval (CI) within each subgroup. Summaries of the primary efficacy variable by treatment arm and subgroup will be produced.

4.7.1.7 Exploratory Analyses

In order to evaluate if the timing of post-baseline radiological scan influenced the primary outcome, the time from randomization to post-radiological scan will be calculated and an exploratory analyses will be conducted. Mean and standard deviation of radiological scan time will be presented by treatment arms and cycle time. Long-Rank test will be used to test if cumulative percentages (survival curve) are equal (median time to each cycle from randomization) by treatment arms.

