7.1.5 Every 8 weeks from Cycle 1, Day 1 (± 3 days)

Every 8 weeks (± 3 days), the following procedures and evaluations will be performed:

- Disease/response assessment (CT scan or MRI scan)

The assessment should be done during scheduled visits where appropriate and possible.

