- b) Subjects who have no tumor assessment after randomization will have PFS censored at the date of randomization, unless they died before the second scheduled tumor assessment.

Further details and other cases will be described in the statistical analysis plan (SAP).

Analysis of Secondary Endpoints

The secondary endpoints (OS, ORR, and DoR) will be analyzed using the investigator and independent radiological review assessments. The degree of agreement between the investigator and the independent assessment of responses will also be summarized and presented in a table.

The first secondary analysis will compare the OS between the 2 treatment arms by using stratified Log-rank test and the stratification factors included in the primary analysis. An interim OS analysis will be carried out at the time of the Final PFS analysis.

Duration of response (DoR) will be analyzed using the same method as for the progression-free survival.

The proportion of subjects achieving confirmed ORR (complete response [CR]+partial response [PR]) will be summarized and presented by treatment arms and cycle and will be compared between the two treatment arms using Cochran-Mantel-Haenszel (CMH) test with the same stratification factors used for the PFS analysis.

Exploratory Analyses

In order to evaluate if the timing of post-baseline radiological scan influenced the primary outcome, the time from randomization to post-radiological scan will be calculated and an exploratory analyses will be conducted. Means and standard deviation of radiological scan time will be presented by treatment arms and cycle time. Log-rank test will be used to test if cumulative percentages (survival curves) are equal (median time to each cycle from randomization) by treatment arms.

Subgroup Analyses

PFS subgroup analyses by gender, race, and age (< 65 years and \geq 65 years) will be carried out using separate unadjusted Log-rank test for the ITT population.

Definition of Efficacy Endpoints

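### The planned scan-timing check compares time to each scan by arm but never uses PFS, so it cannot show how far timing moved the hazard ratio, and its risk set is not defined

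*SAP*

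**What the plan says.** The aim in SAP 4.7.1.7 is "to evaluate if the timing of post-baseline radiological scan influenced the primary outcome". Three steps follow:

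- A time variable: "the time from randomization to post-radiological scan will be calculated and an exploratory analyses will be conducted".
- A description: "Mean and standard deviation of radiological scan time will be presented by treatment arms and cycle time".
- A test: "Long-Rank test will be used to test if cumulative percentages (survival curve) are equal", by arm, with a bracketed reference to the median time from randomization to each cycle.

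Protocol 14.3.4 (Exploratory Analyses) states the same aim and the same test: "Log-rank test will be used to test if cumulative percentages (survival curves) are equal". Neither document says how subjects who progress, die or leave before a given scan enter the test. Neither gives a significance level or says how a timing difference would be related to the PFS result.

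Scans are scheduled from first dose (Protocol 7.1.5: "Every 8 weeks (± 3 days), the following procedures and evaluations will be performed"). PFS is counted from randomization, and dosing may start up to 14 days later (Protocol 5.4.2). Scanning stops once progression is confirmed by independent review (Protocol 9.1).

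The four PFS sensitivity analyses in SAP 4.7.2 deal with other matters. The first uses investigator assessment plus clinical progression. The second and third widen the definition of an event. The fourth backdates progression that follows missed or not-evaluable scans.

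**The concern.** The question is about influence on PFS, but the test looks only at timing. If it rejects, the arms were scanned on different calendars, and the reader still does not know whether the hazard ratio moved by 1% or 10%. If it does not reject, that is only indirect reassurance.

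The trial is open-label and progression is dated by the scan that shows it. If one arm is scanned later, its progressions are dated later and its PFS looks longer. That makes the question worth asking, and this is the only planned analysis that asks it.

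The second problem is the undefined risk set. Subjects who progress have no later scans, so the share of randomized subjects who reach scan 2, scan 3 and so on depends on PFS itself. Read literally, a comparison of cumulative percentages would then partly measure the treatment effect.

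**Working it through.** **Design inputs (SAP 4.9; Protocol 5.2, 5.4.2 and 7.1.5).** 161 subjects per arm; median PFS 4 and 6 months; 15 months' enrolment plus 6 months' follow-up; 3% dropout; scans every 56 days ± 3 from first dose; first dose 0-14 days after randomization.

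**The plan's own figure.** Required events = 4(1.960 + 1.282)² / (ln 1.5)² = 4 × 10.507 / 0.1644 = 255.65. This agrees with the stated 255 events for 90% power, so the design inputs are consistent.

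**Why later scans carry the PFS effect.** Assume exponential PFS and a start delay uniform over 0-14 days (mean 7). With 30.44 days to a month, the medians are 121.8 and 182.6 days. Scan 1 falls on average at day 7 + 56 = 63. A subject has scan 2 only if still progression-free at scan 1:

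- sorafenib: 0.5^(63/121.8) = 0.70
- tivozanib: 0.5^(63/182.6) = 0.79

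For scan 3 the relevant day is 63 + 56 = 119, giving 0.51 and 0.64. The arms differ in the percentage reaching a scan although their calendars are identical.

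**Simulation with identical timing.** 1,000 trials per setting, with progression dated at the next scan. The test is two-sided at 0.05, an assumed level because the SAP gives none.

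| Scan | Reached, sorafenib | Reached, tivozanib | Rejects: progressors kept in denominator | Rejects: censored when scanning ends |
|---|---|---|---|---|
| 1 | 100% | 99% | 4.3% | 4.3% |
| 2 | 69% | 78% | 39.4% | 5.0% |
| 3 | 50% | 63% | 61.3% | 3.2% |
| 4 | 33% | 45% | 68.2% | 5.5% |
| 5 | 20% | 31% | 65.2% | 3.8% |
| 6 | 12% | 21% | 61.0% | 6.2% |

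With progressors kept in, the rates at scans 2 and 3 are 34.8% and 57.2% with no start delay, and 40.0% and 63.9% if 20% of events are deaths. With equal PFS in both arms (4 v 4 months) they are nominal (4.5-5.7%), so the excess comes from the PFS difference.

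**Simulation with every tivozanib scan 7 days late.** The scan-dated hazard ratio moves from 0.67 to 0.61. With no true effect it moves from 1.00 to 0.90.

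- Censored when scanning ends: the shift is detected in at least 99.9% of trials at every scan.
- Progressors kept in: rejection at scans 1-6 is 100, 50.7, 6.6, 17.4, 34.0 and 40.0%. At scan 3 the delay and the PFS effect nearly cancel.
- Mean scan day by arm differs by 7 days at every scan, so the descriptive table shows the shift.

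If the 7-day delay begins only at scan 3 (hazard ratio 0.64), the version with progressors kept in rejects in 5.4% of trials at that scan. The mean scan days still show the 7-day difference.

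**Does an interval-censored model answer the question?** 400 trials per setting; Weibull model, unstratified, no deaths or dropout:

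| True medians (months) | Tivozanib shift | Scan-dated Cox HR | Interval-censored HR |
|---|---|---|---|
| 4 v 6 | 0 days | 0.68 | 0.67 |
| 4 v 6 | 7 days | 0.61 | 0.66 |
| 4 v 4 | 7 days | 0.89 | 0.99 |

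The interval-censored estimate stays close to the true value (0.67 or 1.00). Its gap from the scan-dated hazard ratio is a direct estimate of what timing did.

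**The case against.** The strongest defence is that the test is a screen. If scan timing is balanced by arm, it cannot have dated progression differently between arms. The reference to a survival curve and to median time suggests an ordinary Kaplan-Meier comparison with subjects censored when scanning ends. On that reading the test behaves well scan by scan. The means and SDs would show the size of any shift beside the p-value, and the analysis is exploratory with no decision attached.

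Most of this stands. A reader might infer that the planned test will raise false alarms and miss shifts that matter, so that the study report would misjudge the primary result. The documents do not support that. It needs a risk set the SAP does not fix. Even with progressors kept in the denominator, scan 1 has nominal error and catches a delay of 3 days or more that starts there in every simulated trial. A shift that starts later would still appear in the mean scan days.

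The defence leaves two things unanswered. A screen for balance gives no estimate of the effect on the hazard ratio, which is the stated aim. The choice between two readings with very different behaviour is also left open. Even with censoring, six unadjusted tests give at least one false positive in about 20-27% of trials.

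**Conclusion.** The point holds in limited form and is minor. On any reading, the test cannot answer the question the SAP and protocol set for it, and no other planned analysis covers scans that were done but shifted. The effect at issue is not negligible: a 7-day difference between arms alone moves the hazard ratio from about 0.67 to 0.61, or from 1.00 to about 0.90 with no true effect.

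The confounding with PFS (roughly 35-40% rejection at scan 2 and about 60% at scan 3 with identical timing) arises only if subjects who have progressed stay in the denominator. It does not arise with censoring when scanning ends. The primary log-rank test is unaffected.

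These figures assume exponential PFS at the design medians, a 0-14 day start delay, scan variation within ± 3 days and a two-sided 0.05 level. The shift sizes are illustrations. Nothing in the documents says that a shift occurred. Monte Carlo error in the rejection rates is at most about 1.6 percentage points.

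**What to change.** In SAP 4.7.1.7, add an exploratory interval-censored PFS analysis:

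- Progression lies between the last progression-free independent-review scan (randomization, if progression is seen at the first scan) and the first scan showing progression.
- Deaths enter at their exact dates.
- Strata are those of the primary analysis (IMDC risk category and prior therapy).
- Its hazard ratio and 95% CI are reported beside the primary hazard ratio, and the difference is read as the influence of scan timing.

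Keep the mean and SD of scan times by arm as description. Drop the log-rank timing test, or state that each subject is censored when scanning ends, give the significance level, and say that the results are not adjusted for multiple scans.

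The cost is one extra model, a little programming and a matching wording change in the exploratory part of Protocol 14.3.4. No new data are needed.
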